## 6. DOSING DELAYS/DOSE MODIFICATIONS

The descriptions and grading scales found in the revised NCI Common Terminology Criteria for Adverse Events (CTCAE) version 4.0 will be utilized for dose delays and dose modifications. A copy of the CTCAE version 4.0 can be downloaded from the CTEP website.

[http://ctep.cancer.gov/protocolDevelopment/electronic\\_applications/ctc.htm](http://ctep.cancer.gov/protocolDevelopment/electronic_applications/ctc.htm).

Pembrolizumab will be withheld for drug-related Grade 4 hematologic toxicities, non-hematological toxicity  $\geq$  Grade 3 including laboratory abnormalities despite appropriate replacement therapies when appropriate, and severe or life-threatening AEs as per Table 5.

Table 5 Dose modification guidelines for drug-related adverse events

Toxicity	Hold Treatment For Grade	Timing for Restarting Treatment	Treatment Discontinuation
Diarrhea/Colitis	2-3	Toxicity resolves to Grade 0-1	Toxicity does not resolve within 12 weeks of last dose or inability to reduce corticosteroid to 10 mg or less of prednisone or equivalent per day within 12 weeks
	4	Permanently discontinue	Permanently discontinue
AST, ALT, or Increased Bilirubin	2	Toxicity resolves to Grade 0-1	Toxicity does not resolve within 12 weeks of last dose
	3-4	Permanently discontinue (see exception below) a	Permanently discontinue
Type 1 diabetes mellitus (if new onset) or Hyperglycemia	T1DM or 3-4	Hold pembrolizumab for new onset Type 1 diabetes mellitus or Grade 3-4 hyperglycemia associated with evidence of beta cell failure	Resume pembrolizumab when patients are clinically and metabolically stable
Hypophysitis	2-4	Toxicity resolves to Grade 0-1. Therapy with pembrolizumab can be continued while endocrine replacement therapy is instituted	Toxicity does not resolve within 12 weeks of last dose or inability to reduce corticosteroid to 10 mg or less of prednisone or equivalent per day within 12 weeks
Hyperthyroidism	3	Toxicity resolves to Grade 0-1	Toxicity does not resolve within 12 weeks of last dose or inability to reduce corticosteroid to 10 mg or less of prednisone or equivalent per day within 12 weeks
	4	Permanently discontinue	Permanently discontinue
Hypothyroidism		Therapy with pembrolizumab can be continued while thyroid replacement therapy is instituted	Therapy with pembrolizumab can be continued while thyroid replacement therapy is instituted
Infusion Reaction	2 b	Toxicity resolves to Grade 0-1	Permanently discontinue if toxicity develops despite adequate premedication
	3-4	Permanently discontinue	Permanently discontinue
Pneumonitis	2	Toxicity resolves to Grade 0-1	Toxicity does not resolve within 12 weeks of last dose or inability to reduce corticosteroid to 10 mg or less of prednisone or equivalent per day within 12 weeks

Toxicity	Hold Treatment For Grade	Timing for Restarting Treatment	Treatment Discontinuation
	3-4	Permanently discontinue	Permanently discontinue
Renal Failure or Nephritis	2	Toxicity resolves to Grade 0-1	Toxicity does not resolve within 12 weeks of last dose or inability to reduce corticosteroid to 10 mg or less of prednisone or equivalent per day within 12 weeks
	3-4	Permanently discontinue	Permanently discontinue
All Other Drug-Related Toxicity c	3 or Severe	Toxicity resolves to Grade 0-1	Toxicity does not resolve within 12 weeks of last dose or inability to reduce corticosteroid to 10 mg or less of prednisone or equivalent per day within 12 weeks
	4	Permanently discontinue	Permanently discontinue

Note: Permanently discontinue for any severe or Grade 3 drug-related AE that recurs or any life-threatening event.
 
a For patients with liver metastasis who begin treatment with Grade 2 AST or ALT, if AST or ALT increases by greater than or equal to 50% relative to baseline and lasts for at least 1 week then patients should be discontinued.
 
b If symptoms resolve within one hour of stopping drug infusion, the infusion may be restarted at 50% of the original infusion rate (e.g., from 100 mL/hr to 50 mL/hr). Otherwise dosing will be held until symptoms resolve and the subject should be premedicated for the next scheduled dose; Refer to
 
Table – Infusion Treatment Guidelines for further management details.
 
c Patients with intolerable or persistent Grade 2 drug-related AE may hold study medication at physician discretion. Permanently discontinue study drug for persistent Grade 2 adverse reactions for which treatment with study drug has been held, that do not recover to Grade 0-1 within 12 weeks of the last dose.
			

Dosing interruptions are permitted in the case of medical / surgical events or logistical reasons not related to study therapy (e.g., elective surgery, unrelated medical events, patient vacation, and/or holidays). Subjects should be placed back on study therapy within 3 weeks of the scheduled interruption, unless otherwise discussed with the PI of the study. The reason for interruption should be documented in the patient's study record.

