#### **Secondary Endpoints:**

1. Toxicity by CTCAE criteria (grade 3 or higher hematologic toxicity; grade 3 or higher neurologic toxicity)
2. Overall survival
3. Intracranial response as defined by RANO criteria

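### Section 6's opening sentence sets a separate hematologic hold threshold that Table 5 does not contain, so drug-related Grade 3 and Grade 4 hematologic toxicity have no single dosing rule

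*Combined protocol and SAP*

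**What the plan says.** The opening sentence of Section 6 has three limbs. The first two set thresholds by class: "Pembrolizumab will be withheld for drug-related Grade 4 hematologic toxicities, non-hematological toxicity" at Grade 3 or above. The sentence then continues: "including laboratory abnormalities despite appropriate replacement therapies when appropriate, and severe or life-threatening AEs as per Table 5".

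Table 5 is organised by named toxicity and has no hematologic row. Its last row, "All Other Drug-Related Toxicity", lists Grade 3 or severe events as a hold until recovery to Grade 0-1, and Grade 4 events as a permanent stop. A note under the table adds a permanent stop for any life-threatening event. Grades that lead to a hold and grades that lead to a permanent stop share one column, headed "Hold Treatment For Grade". The hypothyroidism row lists no grade in that column and says "Therapy with pembrolizumab can be continued while thyroid replacement therapy is instituted".

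Table 4 (Section 5.5) covers immune-related events. It has no named hematologic row either, but its catch-all row withholds or discontinues at Grade 3 according to the type of event, and permanently discontinues at Grade 4. Its hypothyroidism row continues drug at Grades 2-4.

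Section 13.2 lists "grade 3 or higher hematologic toxicity" as one of two toxicity categories in the secondary endpoint.

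**The concern.** The sentence gives hematologic toxicity its own, higher threshold. That has a purpose only if Grade 3 hematologic events are meant to be handled differently from other Grade 3 events. The table it introduces handles them identically. Two investigators who each follow Section 6 could therefore act differently on the same event. At Grade 3, one could carry on dosing while the other holds. At Grade 4, one could hold and later restart while the other ends treatment.

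What is at stake is a consistent safety rule and the amount of drug that affected patients receive. The matter deserves attention because hematologic toxicity is one of the few toxicities that the plan singles out for reporting.

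**Working it through.** No sample size, power or event count enters, so the check is a comparison of texts. Drug-related events only:

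| Event | Section 6 sentence | Table 5 | Table 4, if immune-related |
|---|---|---|---|
| Grade 3 hematologic | Below the hematologic threshold of Grade 4 | Catch-all: hold | Catch-all: withhold or discontinue, by type |
| Grade 4 hematologic | Withheld | Catch-all: permanent stop | Catch-all: permanent stop |
| Grade 4 laboratory abnormality with no row of its own | Withheld | Catch-all: permanent stop | Catch-all: permanent stop |
| Grade 3-4 hypothyroidism | Withheld, if read literally | No hold grade; may continue | Continue |
| Grade 3 non-hematologic with no row of its own | Withheld | Catch-all: hold | Catch-all: withhold or discontinue, by type |

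1. Row 1 is a difference of threshold: Grade 4 in the sentence, Grade 3 in the table.

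2. Rows 2 and 3 are a difference of action. Table 4 treats withholding and permanent discontinuation as separate actions, and its general instructions describe resumption after withholding. In the protocol's own usage, then, the two words are not interchangeable.

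3. Row 4 is weaker. The sentence carries a qualifier about replacement therapies. If that qualifier reaches thyroid hormone replacement, the conflict largely disappears, but its scope is unclear.

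4. In row 5 the sentence and Table 5 agree. A Table 5 hold is not in itself a contradiction.

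5. Precedence: the reference to Table 5 is attached to the third limb, not clearly to the two class thresholds. No passage states which text governs.

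Illustration of exposure, not an estimate. Dosing every 3 weeks from week 0 to week 24 gives 24/3 + 1 = 9 scheduled doses, taking six months as 26 weeks. If the event follows dose k, a permanent stop leaves k doses, while a hold with prompt recovery leaves at most 9. The gap is at most 9 - k, that is, from 8 doses (k = 1) down to 1 dose (k = 8). For k = 3 it is 3 doses against at most 9. Any dose lost during the hold narrows the gap.

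**The case against.** The best defence is that the sentence is a general lead-in and Table 5 decides what follows. Three things support it. The table puts grades that end in a permanent stop under a heading about holding, so withholding can be read as the first step. Section 5.5 uses the same word to introduce Table 4, which also contains permanent stops. And the note on life-threatening events, read with the Grade 4 definition in Table 6 (Section 7.5), points the same way as the catch-all row; the sentence itself never says that drug may restart. This softens the Grade 4 difference considerably. It does not explain why the sentence states a hematologic threshold that the table lacks.

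At Grade 3, Table 6 describes the grade as severe, so the third limb could be read to reach Grade 3 hematologic events through Table 5. On that reading the separate Grade 4 hematologic threshold has no function, so a drafting mismatch remains.

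On hypothyroidism, the text of Section 5.5, Table 4 and Table 5 point in one direction, and a specific row would ordinarily be followed over a general sentence. That is why the point is secondary here.

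Two stronger readings are tempting but unsupported. A reader might infer that the sentence withholds drug only for the two classes; the third limb shows otherwise. A reader might also infer that Table 4 offers nothing for cytopenias; its catch-all row reaches immune-related ones. In addition, Section 5.5 asks that immune-related events of Grade 2 or higher be discussed at once with the overall principal investigator or designee, which limits divergence between sites for those events.

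**Conclusion.** The mismatch is real and narrow. It is clearest for the hematologic threshold (Grade 3). It is present but softened for Grade 4 hematologic toxicity and unlisted Grade 4 laboratory abnormalities, and weakest for hypothyroidism. It rests on reading cytopenias into Table 5's catch-all row, which is where that table leaves them, and on the absence of a precedence rule.

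Its consequence is for dosing decisions and exposure. The documents give no expected rate of drug-related Grade 3-4 cytopenia, so the number of patients affected is unknown.

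A reader might infer that the secondary endpoint or PFS6 is distorted, for instance by treating each affected patient as 1/24 = 4.2% of the evaluable sample in error. The documents do not support that. Section 13.7 reports the proportion with Grade 3 or higher toxicity whatever was done with the drug. Under Section 13.2, PFS6 depends on progression or death, not on stopping treatment. Sections 5.13 and 12.1.3 and the active follow-up footnote to the Section 10 calendar continue disease follow-up after drug is stopped without progression. An indirect effect of lower exposure on outcome is conceivable, but nothing in the documents lets it be sized.

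**What to change.** Reconcile the opening sentence of Section 6 with Table 5, and with Table 4 where it overlaps, for four items: Grade 3 hematologic toxicity, Grade 4 hematologic toxicity, Grade 4 laboratory abnormalities without their own row, and Grade 3-4 hypothyroidism. This can be done by taking the class thresholds out of the sentence and referring wholly to the tables, or by adding rows to the tables so that they match whatever the sentence is meant to say. In either case, state which text governs if they differ, and make clear how far the replacement-therapy qualifier extends. Which action applies at each grade is a clinical decision for the sponsor, and no view is taken here.

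The cost is one paragraph or a few table rows in an amendment. It adds no assessments and changes neither the sample size nor the analysis.

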### 5.5 Supportive Care Guidelines for Immune Related Adverse Events (irAEs)

Adverse events (both non-serious and serious) associated with pembrolizumab exposure may represent an immunologic etiology. These adverse events may occur shortly after the first dose or several months after the last dose of treatment. Pembrolizumab must be withheld for drug-related toxicities and severe or life-threatening AEs as per the Table below. See Section 6.0 for supportive care guidelines, including use of corticosteroids.

Subjects should receive appropriate supportive care measures as deemed necessary by the treating investigator. Suggested supportive care measures for the management of adverse events with potential immunologic etiology are outlined below and in greater detail in the ECI guidance document. Where appropriate, these guidelines include the use of oral or intravenous treatment with corticosteroids as well as additional anti-inflammatory agents if symptoms do not improve with administration of corticosteroids. Note that several courses of steroid tapering may be necessary as symptoms may worsen when the steroid dose is decreased.

If an irAE is suspected, efforts should be made to rule out neoplastic, infectious, metabolic, toxin or other etiologic causes prior to labeling an adverse event as an irAE. Subjects who develop a Grade 2 or higher irAE should be discussed immediately with the overall Principal Investigator or designee. The treatment guidelines are intended to be applied when the investigator determines the events to be related to pembrolizumab.

It may be necessary to perform conditional procedures such as bronchoscopy, endoscopy, or skin photography as part of evaluation of the event. Suggested conditional procedures, as appropriate, can be found in the ECI guidance document.

Note: if after the evaluation the event is determined not to be related, the investigator does not need to follow the treatment guidance (as outlined below). Refer to Section 6.0 for dose modification.

- **Pneumonitis:**
  - For **Grade 2 events**, treat with systemic corticosteroids. When symptoms improve to Grade 1 or less, steroid taper should be started and continued over no less than 4 weeks.
  - For **Grade 3-4 events**, immediately treat with intravenous steroids. Administer additional anti-inflammatory measures, as needed.
  - Add prophylactic antibiotics for opportunistic infections in the case of prolonged steroid administration.
  

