  - For **Grade 2** events, treat with corticosteroids.
  - For **Grade 3-4** events, treat with systemic corticosteroids.
  - When symptoms improve to Grade 1 or less, steroid taper should be started and continued over no less than 4 weeks.
- **Cerebral Edema**

Due to the immunologic nature of pembrolizumab administration, cerebral edema could theoretically result as a consequence of pembrolizumab administration due to immune infiltration of the brain. Symptoms related to cerebral edema may include headache or neurologic deficit that is either new or worsened. Patients with any signs or symptoms of cerebral edema should be treated as clinically appropriate including initiation or increased systemic corticosteroid dosing, treatment with an osmotic diuretic or surgical decompression. Subsequent pembrolizumab dosing should be immediately interrupted if significant clinical symptoms attributable to cerebral edema develop. Treatment with additional pembrolizumab doses may only be re-initiated if clinically significant symptoms attributable to cerebral edema have resolved to grade  $\leq 1$  or pre-treatment baseline. Patients who develop CTCAE 4.0 grade-4 cerebral edema attributable to pembrolizumab administration should not receive further pembrolizumab doses and should discontinue study therapy.

Recommendations to manage irAEs not detailed elsewhere in the protocol are detailed in Table 4.

Table 4 Dose Modification and Toxicity Management Guidelines for Immune-related AEs Associated with Pembrolizumab

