**General instructions:**

1. Corticosteroid taper should be initiated upon AE improving to Grade 1 or less and continue to taper over at least 4 weeks.
2. For situations where pembrolizumab has been withheld, pembrolizumab can be resumed after AE has been reduced to Grade 1 or 0 and corticosteroid has been tapered. Pembrolizumab should be permanently discontinued if AE does not resolve within 12 weeks of last dose or corticosteroids cannot be reduced to  $\leq 10$  mg prednisone or equivalent per day within 12 weeks.
3. For severe and life-threatening irAEs, IV corticosteroid should be initiated first followed by oral steroid. Other immunosuppressive treatment should be initiated if irAEs cannot be controlled by corticosteroids.

Immune-related AEs	Toxicity grade or conditions (CTCAEv 4.0)	Action taken to pembrolizumab	irAE management with corticosteroid and/or other therapies	Monitor and follow-up
Pneumonitis	Grade 2	Withhold	
 
• Administer corticosteroids (initial dose of 1-2 mg/kg prednisone or equivalent) followed by taper
 
	
 
• Monitor participants for signs and symptoms of pneumonitis
 
• Evaluate participants with suspected pneumonitis with radiographic imaging and initiate corticosteroid treatment
 
• Add prophylactic antibiotics for opportunistic infections
 

	Grade 3 or 4, or recurrent Grade 2	Permanently discontinue		
Diarrhea / Colitis	Grade 2 or 3	Withhold	
 
• Administer corticosteroids (initial dose of 1-2 mg/kg prednisone or equivalent) followed by taper
 
	
 
• Monitor participants for signs and symptoms of enterocolitis (ie, diarrhea, abdominal pain, blood or mucus in stool with or without fever) and of bowel perforation (ie, peritoneal signs and ileus).
 
• Participants with <math>\geq</math> Grade 2 diarrhea suspecting colitis should consider GI consultation and performing endoscopy to rule out colitis.
 
• Participants with diarrhea/colitis should be advised to drink liberal quantities of clear fluids. If sufficient oral fluid intake is not feasible, fluid and electrolytes should be substituted via IV infusion.
 

	Grade 4	Permanently discontinue		

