Myocarditis	Grade 1 or 2	Withhold	
 
Based on severity of AE administer corticosteroids
 
	
 
Ensure adequate evaluation to confirm etiology and/or exclude other causes
 

	Grade 3 or 4	Permanently discontinue		
All other immune-related AEs	Intolerable/persistent Grade 2	Withhold	
 
Based on type and severity of AE administer corticosteroids
 
	
 
Ensure adequate evaluation to confirm etiology and/or exclude other causes
 

	Grade 3	Withhold or discontinue based on the type of event. Events that require discontinuation include and not limited to: Guillain-Barre		

		Syndrome, encephalitis		
	Grade 4 or recurrent Grade 3	Permanently discontinue		

1. Withhold or permanently discontinue pembrolizumab is at the discretion of the investigator or treating physician.
 
NOTE:          For participants with Grade 3 or 4 immune-related endocrinopathy where withhold of pembrolizumab is required, pembrolizumab may be resumed when AE resolves to <math>\leq</math> Grade 2 and is controlled with hormonal replacement therapy or achieved metabolic control (in case of T1DM).
				

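### Table 4 and Table 5 (with its Note) give different stop or restart instructions for a few adverse events, and the protocol does not say plainly which table governs

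*Combined protocol and SAP*

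**What the plan says.** Section 5.5 introduces the immune-related rules with "Pembrolizumab must be withheld for drug-related toxicities and severe or life-threatening AEs as per the Table below". The only table in that section is Table 4. Its lead-in then describes it as residual: "Recommendations to manage irAEs not detailed elsewhere in the protocol are detailed in Table 4".

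Section 6 carries a near-identical instruction that ends at the other table: "including laboratory abnormalities despite appropriate replacement therapies when appropriate, and severe or life-threatening AEs as per Table 5". Table 5 follows, with one row per toxicity, a catch-all row, and a Note: "Permanently discontinue for any severe or Grade 3 drug-related AE that recurs or any life-threatening event".

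Table 4 writes recurrence into two of its rows. For pneumonitis, permanent discontinuation applies to "Grade 3 or 4, or recurrent Grade 2"; for all other immune-related events, to "Grade 4 or recurrent Grade 3". Table 5 handles recurrence only through its Note.

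There is one safeguard in Section 5.5: "Subjects who develop a Grade 2 or higher irAE should be discussed immediately with the overall Principal Investigator or designee".

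**The concern.** Both tables prescribe the dosing action, and most events appear in both. Where they differ, a site can comply fully with one and re-dose a patient whom the other says to stop. The clearest example is a second Grade 2 pneumonitis. Two sites could also treat the same event differently, which would make the treatment and toxicity experience harder to interpret in a single-arm trial aiming for 24 evaluable patients.

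What is at stake is patient safety and uniform conduct. The PFS6 definition, the sample size and the decision rule (at least 10 of 24) do not depend on these rules.

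**Working it through.** No arithmetic figure in the plan is in question, so the check is a row-by-row comparison of Table 4, the Table 5 rows, the Note and the Section 6 text.

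| Event | Table 4 (Section 5.5) | Table 5 row (Section 6) | Table 5 Note |
|---|---|---|---|
| Recurrent Grade 2 pneumonitis | Stop permanently | Hold Grade 2, restart at Grade 0-1; recurrence not mentioned | Not reached: recurrence is limited to severe or Grade 3 |
| Grade 4 hyperthyroidism | Hold or stop, at the physician's discretion (footnote 1) | Stop permanently | Stop, if life-threatening means Grade 4 |
| Grade 4 hypophysitis | Hold or stop, at discretion | Hold, restart at Grade 0-1; may continue during hormone replacement | Stop, if life-threatening means Grade 4 |
| Grade 4 hyperglycemia with beta-cell failure | Hold; may resume with metabolic control | Hold; resume when stable | Stop, if life-threatening means Grade 4 |
| Grade 4 hypothyroidism | Continue with replacement | Continue with replacement; no grade limit | Stop, if life-threatening means Grade 4 |

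**Differences as written: 2.** These are the first two rows. Neither depends on how the Note is read.

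**Conditional differences: 3.** These are the last three rows. Table 6 (Section 7.5) words Grade 4 in terms of life-threatening consequences, which supports the reading that creates them. The same table's seriousness definition is narrower: immediate risk of death, in the investigator's view, from the event as it occurred. The Note does not say which applies. The total is therefore 2 under the narrower meaning and 2 + 3 = 5 under the Grade 4 meaning.

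**Which table governs?**

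- Section 5.4 sends immune-related events to Section 6 and the ECI guidance document for supportive care.
- Section 5.5 sends withholding to Table 4, then refers to Section 6 for supportive care. It also closes its note on unrelated events by referring to Section 6 for dose modification.
- The Table 4 lead-in makes that table residual. Yet 8 of its 10 event groups also have their own Table 5 row; only myocarditis and the all-other group do not. Applied strictly, the lead-in would set aside most of Table 4.
- Section 6 sends severe or life-threatening events to Table 5.

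The pointers lean towards Section 6, but the Section 5.5 sentence on withholding points the other way. If Section 6 did prevail, the pneumonitis rule in force would be hold and restart, which is the less protective of the two. Nor would that settle the Note against the rows, since both sit inside Section 6.

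**The case against.** The strongest reply is that most of this can be read without contradiction. Several pointers favour Section 6. Stopping for Grade 4 hyperthyroidism satisfies both tables, because Table 4's discretion includes stopping; Table 4 likewise permits stopping for Grade 4 hypophysitis. The Table 5 pneumonitis row is silent on recurrence, so a site that follows Table 4 breaches nothing. Immune-related events of Grade 2 or higher go to the overall principal investigator at once.

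Part of this stands. A site that always takes the stricter action stays compliant on pneumonitis and hyperthyroidism. But the protocol does not tell sites to do so. A site working from Section 6 alone finds no stop rule for recurrent Grade 2 pneumonitis, and its Note limits recurrence to worse events. A site that holds a Grade 4 hyperthyroidism under Table 4 breaches Table 5. The discussion with the principal investigator lowers the risk but supplies no deciding rule.

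A reader might infer a longer list of conflicts. The documents do not support three likely additions:

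- **Grade 4 hematologic toxicity.** Section 6 says "Pembrolizumab will be withheld for drug-related Grade 4 hematologic toxicities", while the catch-all row stops permanently. But Table 5 itself lists Grade 4 in its hold column and then gives a permanent stop, so the sentence can be read as the trigger and the row as the duration.
- **Grade 3 hypothyroidism.** The Section 6 hold for non-hematologic Grade 3 or higher is qualified by persistence despite replacement therapy, which fits rows that continue treatment on replacement.
- **Recurrent Grade 3 colitis.** The rows are silent on recurrence and the Note supplies the rule. That is a general rule filling a gap, although Table 4's explicit recurrence wording elsewhere could make the silence look deliberate.

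These three merit clarification but are not conflicts. Grade 3 myocarditis, Guillain-Barre syndrome and encephalitis are also not counted, because the Table 4 lead-in most naturally leaves them to Table 4, which stops treatment.

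**Conclusion.** The point holds in a limited form: two differences in prescribed action as written, and three more if life-threatening in the Note means Grade 4. The most consequential is recurrent Grade 2 pneumonitis, where one table stops the drug and the other allows it to restart. It would be too strong to say that the protocol gives no guidance on precedence; the guidance leans one way but is neither explicit nor consistent.

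The conclusion assumes that the table mentioned at the start of Section 5.5 is Table 4. It also assumes that the ECI guidance document (Appendix B), whose text is not available here, does not already set a precedence rule; that cannot be excluded. Aligning the tables is worth doing because it is cheap and prevents re-dosing that another part of the protocol forbids.

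**What to change.** Change wording only:

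1. In the Table 5 pneumonitis row, add permanent discontinuation for recurrent Grade 2.
2. Make the Grade 4 hyperthyroidism action the same in both tables, with the sponsor and drug supplier confirming which one.
3. Define life-threatening in the Note. State that the Note does not override the hypothyroidism, hypophysitis and T1DM/hyperglycemia rows when the event is controlled by hormone replacement or metabolic control.
4. State which table governs immune-related events, and that the stricter action applies where the tables still differ, subject to the exception in step 3.

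The same amendment could tidy the Grade 4 hematologic, Grade 3 hypothyroidism and recurrent Grade 3 colitis wording.

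The cost is a protocol wording amendment, with no added procedures, visits or patients. The downside is that a few patients may stop treatment who could otherwise have been re-dosed.
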